## II. SPECIFIC AIMS

The specific aims of this study are:

**AIM 1:** To use high-density EEG recordings to characterize the different brain-states induced by the anesthetic vapor, sevoflurane.

**Hypothesis 1a.** The onset and stable maintenance of sevoflurane-induced beta oscillations will signify a sedative brain state with a probability of response to auditory and nociceptive stimuli that approaches the awake state.

**Hypothesis 1b.** The onset and stable maintenance of highly coherent sevoflurane-induced frontal alpha and theta oscillations will signify a brain-state approaching a zero probability of response to auditory and nociceptive stimuli.

**Hypothesis 1c.** Sevoflurane-induced large slow oscillations (at maximum amplitude) and burst suppression will signify a brain state with a zero probability of response to auditory stimuli.

**Hypothesis 1d.** Return of consciousness will be preceded by return of gamma oscillations and the loss of large amplitude slow, theta, alpha and beta oscillations.

**AIM 2:** To use high-density EEG recordings to understand the neural-circuit mechanism of action of ether anesthetics.

**Hypothesis 2a.** The administration of an N-methyl-D-aspartate receptor antagonist (ketamine) during sevoflurane-induced unconsciousness (putative  $\gamma$ -aminobutyric acid mechanism) will antagonize and significantly diminish the amplitude of the alpha and slow oscillations.

**Hypothesis 2b.** The administration of an N-methyl-D-aspartate receptor antagonist (ketamine) during sevoflurane-induced unconsciousness (putative  $\gamma$ -aminobutyric acid mechanism) will produce globally non-coherent beta oscillations that are sufficient to maintain a brain state with a zero probability of response to auditory stimuli.

**Hypothesis 2c.** The administration of an N-methyl-D-aspartate receptor antagonist (ketamine) during sevoflurane-induced unconsciousness (putative  $\gamma$ -aminobutyric acid mechanism) will antagonize the effects of sevoflurane on airway collapsibility by mediated by  $\gamma$ -aminobutyric acid inhibition on the hypoglossal motor neuron.

**AIM 3:** To use inflammatory profiling of serum to understand the effect of sevoflurane on systemic inflammation

**Hypothesis 3a:** We hypothesize that sevoflurane-anesthesia will be associated with increased levels of pro-inflammatory cytokines interleukin 6 and TNF-alpha.

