**Study Visit 1 and 2:**

Study subjects will arrive at the study site and confirmation of the study subjects' fasting status (minimum 8 hours) will be made. A urine sample will be obtained for a toxic substance screen and for female study subjects, pregnancy testing.

Blood Draws: For all subjects, we will acquire blood samples during Study Visits 1 and 2. The blood draws taken before and after anesthetic exposure will comprise the following: 1.) approximately 2 ml of whole blood for analysis using the 44-analyte TruCultureMAP. Analytes in this map include interleukin 6 and TNF-alpha and, 2.) approximately 13 ml of blood will be acquired processed into serum and stored for downstream studies and

confirmatory assays of TruCultureMAP results.

An EEG montage with a maximum of 256 channels will be placed on the subject. Standard physiological monitors for anesthesia will be placed including: electrocardiogram, pulse oximeter, and non-invasive blood-pressure cuff. End-tidal CO2 measurements will be made by way of a capnogram attached to the expiratory port on the breathing circuit. Galvanic skin response will also be measured. A cuff pain delivery device will be attached to the gastrocnemius area of the lower leg. Baseline vital signs will then be taken. A peripheral intravenous line will be placed and an infusion of ringer's lactate or normal saline will be started. Baseline physiologic measurements will be taken.

The study protocol will be divided into 3 segments. These segments are defined in order as: Baseline Recording; Induction and Recovery from Hypnosis; Post-Anesthesia Recovery.

One time before and one time after the study period, a calibrated cuff pain stimuli will be delivered to the gastrocnemius area of the lower leg using a validated cuff pain device titrated to 8-9/10 pain. A computer controlled air compressor (Hokanson Rapid Cuff Inflator) will inflate the cuff to a pre-specified pressure, and maintain the pressure at that level. Pressure will be maintained for up to 5-minutes to evaluate brain, cardiovascular, and subjective response to experimental pain. One advantage to using cuff algometry pain is that unlike more superficial methods (e.g. heat pain), cuff pain responses are unaffected by sensitization or desensitization of the skin, indicating that this procedure primarily assesses sensitivity in muscle and other deep tissues.

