Behavioral Analysis: The probability of response to the click and verbal stimuli and the difference in probability of response will be estimated by using Bayesian Monte Carlo methods to fit a state-space model to these data. To perform group-level analyses, we will align the behavioral data across subjects with respect to each subject's LOC time for induction and with respect to each subject's ROC time for emergence. We will then pool the responses within bins. The pooled data will be used to estimate group-level probabilities of response using the state-space model.

Spectral Analysis: We will compute spectrograms for all subjects using the multitaper method. We will also compute group-level baseline-normalized spectrograms for induction and emergence by taking the median across subjects with the data aligned to the LOC and ROC time points, respectively. To determine if the group-level spectrogram is significantly greater than baseline, we will perform a two-group-test as implemented in chronux.

Eigenvalue and Modal Projection Analyses: We will perform an eigenvector decomposition analysis of the cross-spectral matrix to identify the principal modes of oscillation in the conscious and unconscious states and to analyze how activity within these principal modes change through time. We will estimate the cross-spectral matrices  $P_{\text{baseline}}(f)$  and  $P_{\text{unconscious}}(f)$  at each frequency  $f$  using the multitaper method using data from the full baseline period, and segments of at least 5 min extending from LOC to ROC, respectively, for each subject. An eigenvalue decomposition of the median cross-spectral matrix at each frequency will be performed. Each eigenvector describes a

coherent spatial distribution or mode of oscillation, and the corresponding eigenvalue quantifies the power in this mode. We then use modal projection analysis to characterize how power within principal modes change as a function of time. A permutation-based procedure will be performed to assess statistical significance for the modal projection analysis.

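### The only spectral test stated for emergence asks whether power is above baseline, which does not match Hypothesis 1d's predicted change from the unconscious state before return of consciousness

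*Combined protocol and SAP*

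**What the plan says.** Hypothesis 1d (section II, Specific Aims) reads: "Return of consciousness will be preceded by return of gamma oscillations and the loss of large amplitude slow, theta, alpha and beta oscillations". It contains a change in five bands and an order in time.

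The Spectral Analysis paragraph of section VI computes a spectrogram for every subject, then "group-level baseline-normalized spectrograms for induction and emergence" by "taking the median across subjects with the data aligned to the LOC and ROC time points, respectively". One inference follows, a two-group test from the chronux software, and its purpose is given as: "To determine if the group-level spectrogram is significantly greater than baseline". No alpha is given for it, and no hypothesis is named.

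That paragraph does not define baseline. Two places indicate the awake state. The study segments run in the order "Baseline Recording; Induction and Recovery from Hypnosis; Post-Anesthesia Recovery", and the eigenvalue analysis sets a baseline matrix beside an unconscious one "to identify the principal modes of oscillation in the conscious and unconscious states".

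The same section adds a time-resolved analysis: "We then use modal projection analysis to characterize how power within principal modes change as a function of time". Its significance is to be judged by a permutation procedure that is not described further.

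**The concern.** A test has to match its hypothesis in reference state, direction and timing. Hypothesis 1d concerns the change from unconsciousness to the period just before ROC, upward for gamma and downward for the other four bands. The stated test concerns the difference from baseline, upward, in a group median. If 1d is true, the bands should be moving towards baseline, so the predicted pattern tends towards the test's null result.

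At stake is whether the trial can support or refute 1d. A non-significant result against baseline can mean that the oscillation has gone, or that the sample was too small or noisy to show that it is still there. The stated test does not separate the two. A spectrogram that appears to change before ROC also carries no error rate for the claim of order.

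**Working it through.** **1. Prediction and test side by side.** This takes baseline as awake and takes the word return in 1d to mean that gamma is below its awake level during unconsciousness.

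| Band | Unconscious, relative to baseline | Predicted before ROC | Stated test if 1d is true |
|---|---|---|---|
| Gamma | below | rises towards baseline | non-significant before and after the change |
| Slow, theta, alpha, beta | above | fall | significant, then non-significant if power nears baseline |

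Going from significant to non-significant is not itself a test of the change, since both results are relative to baseline and not to each other.

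**2. Sample sizes.** The only sizing in the plan is for the Global Precedence task: n = (1.645 + 1.282)² × 9 / 3² = 8.56, rounded up to 9, taking 9 as the variance of the within-subject difference. This reproduces the plan's figure but is not tied to 1d. Section VI proposes enrolling 12 and section III selects 24, so several sizes are shown below.

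**3. Direction.** Assume a one-sided 0.05 test in z form, with d the true difference from baseline in SD units: P(reject) = Φ(√n·d − 1.645).

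- d = 0 (band back at baseline): Φ(−1.645) = 0.05 at any n.
- d = −0.5 (gamma suppressed): Φ(−1.5 − 1.645) = 0.0008 at n = 9; Φ(−1.732 − 1.645) = 0.0004 at n = 12.
- d = +0.5 (band still raised): Φ(1.5 − 1.645) = 0.44 at n = 9; Φ(1.732 − 1.645) = 0.53 at n = 12; Φ(2.449 − 1.645) = 0.79 at n = 24.

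Gamma therefore goes from almost no chance of rejection to the false-positive rate, and its recovery leaves no usable signal.

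**4. Non-significance while a band is still raised.** Assume a paired one-sided t-test at 0.05, a residual of 1.5 dB, and an SD of 2 to 4 dB for the within-subject difference. None of these values is in the documents. P(non-significant) = P(T < t₀.₉₅), where T is noncentral t with n − 1 df and noncentrality (1.5/SD)·√n.

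| n | Critical t | SD (dB) | Noncentrality | P(non-significant) |
|---|---|---|---|---|
| 12 | 1.796 | 2 | 2.598 | 0.22 |
| 12 | 1.796 | 4 | 1.299 | 0.67 |
| 24 | 1.714 | 2 | 3.674 | 0.03 |
| 24 | 1.714 | 4 | 1.837 | 0.45 |

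Larger residuals are missed less often. At 3 dB and n = 12, noncentrality is 5.196 (SD 2) or 2.598 (SD 4), giving about 0.001 or 0.22.

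**5. Order.** Section VI aligns spectral and behavioral data to ROC. Alignment allows the sequence to be seen. The section states no change time, latency or order statistic for any EEG band.

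**6. Other analyses.** Modal projection uses baseline and unconscious modes at each frequency and follows them over time, but states no null hypothesis, gamma band or ROC-timed contrast. Phase–amplitude analysis covers 0.1–1 Hz phase and 8–14 Hz amplitude only. The behavioral model estimates response probability and is not linked to band timing.

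**The case against.** The strongest reply is that section VI holds more than this one test. Modal projection is time-resolved, uses modes from the unconscious state, has its own significance procedure and does not exclude gamma. Spectrograms exist for every subject, and so do individual ROC times. This stands to the extent that a reader should not infer that the plan leaves 1d without any relevant analysis or lacks the per-subject data. What it lacks is a stated contrast and order statistic for 1d.

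A reader might also infer that the plan will count non-significance as confirmation of 1d, so that noisier data make the hypothesis look better supported. The documents do not say so. They link no hypothesis to this test, and the same sentence covers induction, where looking for power above baseline suits the onset of oscillations. The risk is of a misreading that the plan does not guard against.

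A third reply is that loss of large-amplitude oscillations need not mean return to baseline, so a residual of 1 or 2 dB may be compatible with 1d. This is a fair reading. It makes an equivalence margin optional and strengthens the case for using the unconscious segment as the reference.

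Finally, the test may be run two-sided despite its wording. Suppressed gamma could then be flagged, but return to baseline would still be the null result and order would still have no test.

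**Conclusion.** The concern holds in this form: the one spectral inference stated for emergence has the wrong reference and direction for Hypothesis 1d, and no order statistic relative to ROC is given. Modal projection could bear on loss of the unconscious modes, but as written it does not specify a test of 1d.

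The mismatch follows from the wording and does not depend on sample size. It rests on baseline meaning the awake recording, which is a firm inference but not stated text. The figures are illustrations only: 0.22 to 0.67 with 12 subjects and 0.03 to 0.45 with 24 depend on an assumed residual, SD, alpha and form of test. More subjects reduce that error but leave the mismatch in place.

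The change is worth making but not critical. Hypothesis 1d is one of four EEG sub-hypotheses under Aim 1 and is not the sample-size endpoint.

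**What to change.** Add a paragraph for Hypothesis 1d to section VI:

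- **Reference.** Use a steady unconscious segment of the same visit. The plan's unconscious segments extend to ROC, so end the reference before the pre-ROC window begins.
- **Change.** Fix the pre-ROC window and band limits in advance. Within each subject, test the change from reference to window in the predicted direction: gamma up; slow, theta, alpha and beta down.
- **Order.** Estimate each subject's change time per band relative to ROC and test lead time above zero across subjects by a signed-rank or sign-flip test. Search on both sides of ROC; a search that stops at ROC makes every lead positive by construction. Auditory stimuli are 4 to 8 seconds apart, which limits how finely ROC is timed.
- **Multiplicity.** There are five band tests. If 1d is claimed only when all five succeed, each can be tested at the full level; if bands are claimed singly, adjust for five.
- **Interpretation.** State that non-significance against baseline is not evidence of loss. A dB equivalence margin is optional.
- **Modal projection.** If it is meant to serve 1d, state its null hypothesis, bands and timing relative to ROC.

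The cost is plan wording and extra analysis of data already to be recorded. Power for order is limited at the smaller size. An exact one-sided sign test needs 10 of 12 subjects leading (level 79/4096 = 0.019), with power 0.56 if 80% of subjects truly lead and 0.89 if 90% do. With 24 it needs 17 (level 0.032), with power 0.91 and 0.998. Those lead proportions are assumptions.

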### III. SUBJECT SELECTION

We will select 24 volunteer subjects (male and female) between the ages of 18-50 years. The subjects will be recruited using:

- An announcement of the study distributed through the Partners Public Affairs distribution list.

All study subjects will be American Society of Anesthesiologists (ASA) physical status classification P1. That is, all study subjects will be fit and healthy. A complete medical history will be taken and a complete physical examination will be given to rule out active and chronic medical problems.

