## **VI. BIostatistical Analysis**

We are using an endpoint of performance score on the Global Precedence task to guide sample size determination. Our null hypothesis is the average within subject difference in performance score for sevoflurane compared to sevoflurane/ketamine is zero. Our

alternative hypothesis is the average within subject difference in performance score for sevoflurane compared to sevoflurane/ketamine is 3. If we assume that the variance in performance score is 9, a type I error of 0.05 and a minimum power of 0.90 for a one-sided z-test, the sample size determinations for our study is 9. Therefore, we should detect a clinically relevant improvement in performance score if we successfully enroll only 9 subjects. To account for data unanticipated events that may lead to poor data quality or data loss, we are proposing to enroll 12 subjects.

EEG acquisition Preprocessing: Continuous EEG will be recorded with up to 256 channels. All data will be stored for subsequent off-line analysis. We will apply an anti-aliasing filter and down-sampled the EEG data to 500 or 250 Hz before analysis. Bandpass filtering of the acquired signal will vary depending upon the features of the EEG data of interest. EEG signals will be remontaged to a nearest-neighbor Laplacian reference, using distances along the scalp surface to weigh neighboring electrode contributions. Trigger signals will be sent from the stimulus delivery system to the EEG recording system to tag the stimulus events for subsequent binning, temporal epoching and averaging of EEG data into the relevant evoked potential averages according to stimulus type and experimental condition.

Video recording to assess level of arousal: Video of the study subject may be recorded during the baseline and induction and recovery from hypnosis periods to assess the study subject's level of arousal. In particular, from clinical experience and previous studies, we note that subjects will exhibit varying levels of arousal after the loss of consciousness, visible in terms of spontaneous movement, which can be recorded on video and then correlated with the EEG. Permission to record video for these data analysis purposes will be obtained from the main research consent form. The video recordings will be stored in a locked file in the investigators office.

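### Eigenvalues of a median cross-spectral matrix are not guaranteed to be mode power; power should be taken from each subject's own matrix

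*Combined protocol and SAP*

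**What the plan says.** The paragraph on eigenvalue and modal projection analyses (Section VI) estimates multitaper cross-spectral matrices separately by subject: one from the whole baseline recording, and one from stretches of five minutes or more between loss and return of consciousness. The next step is: "An eigenvalue decomposition of the median cross-spectral matrix at each frequency will be performed". Each eigenvector is then called a mode of oscillation, and "the corresponding eigenvalue quantifies the power in this mode". No condition is attached to that statement. The modes are carried forward: "We then use modal projection analysis to characterize how power within principal modes change as a function of time". Significance of the projection is assessed by permutation.

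The paragraph does not say whether the median is entrywise or of another kind, or whether it runs over subjects or over time windows. The neighbouring spectrogram analysis does specify "taking the median across subjects with the data aligned to the LOC and ROC time points", but that wording is not repeated for the matrix. There is no check that the median matrix is valid and no rule for a negative eigenvalue. On dimension, "Continuous EEG will be recorded with up to 256 channels".

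**The concern.** A multitaper cross-spectral matrix is Hermitian and positive semidefinite, so for a single subject an eigenvalue is the power along its eigenvector. An entrywise median does not preserve this, because different entries can come from different subjects or windows. The sentence equating eigenvalue and power is then true of each input but not of the matrix that is decomposed.

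At stake is the reported size of each mode. A trailing mode could be given negative power, and the positive eigenvalues would then sum to more than the trace. A leading mode's power could be misstated without any visible sign. Among the analyses described in Section VI, this is the only one that examines relations between channels. It therefore bears on Hypotheses 1b and 2b, which concern coherent and non-coherent oscillations.

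**Working it through.** The plan attaches no numerical figure to this analysis, so there is none to reproduce. The check is algebra, one exact example, and simulation for size.

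**Inputs from the documents.** Up to 256 channels (Section VI). For the number of subjects, Section VI says "we are proposing to enroll 12 subjects", whereas Section III says "We will select 24 volunteer subjects (male and female) between the ages of 18-50 years"; both numbers were tried. The documents give no between-subject EEG variance, so every simulated size below rests on assumption.

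**Algebra.** Let P_i be subject i's matrix at one frequency, M the entrywise median (real and imaginary parts separately), and u a unit eigenvector of M with eigenvalue w.

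- Power of subject i in mode u: u\*P_i u, which is never negative.
- Eigenvalue: w = u\*Mu, a weighted sum of entrywise medians.
- A median of sums is not the sum of medians, so w need not equal the median of u\*P_i u and can fall below zero. For the arithmetic mean matrix, u\*(mean P)u is exactly the mean of u\*P_i u, so the problem does not arise.
- M is still Hermitian, so its eigenvalues are real and its eigenvectors orthonormal.

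**Exact example.** Take three subjects and three channels, each subject with one mode: v = (1,1,1), (1,1,−1), (1,−1,−1). Each matrix vv′ has eigenvalues 3, 0, 0.

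- The off-diagonal medians for channel pairs 1–2, 1–3 and 2–3 are 1, −1 and 1, so M = [[1,1,−1],[1,1,1],[−1,1,1]]. Its eigenvalues are 2, 2, −1 (sum 3, product −4).
- The eigenvector for −1 is u = (1,−1,1)/√3. The power of each subject in it is (u′v)² = (±1/√3)² = 1/3. The eigenvalue says −1; the median power is +1/3.
- In the two leading dimensions each subject has power 3 − 1/3 = 8/3 ≈ 2.67, whereas the two leading eigenvalues sum to 4.
- The mean matrix has eigenvalues 1.33, 1.33, 0.33, none negative.

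**Size by simulation, entrywise median over 12 subjects, 256 channels.**

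| Assumed structure | Negative eigenvalues (% of count) | Their summed size (% of trace) | Leading eigenvalue ÷ median projected power |
|---|---|---|---|
| Common mode as strong as each of three subject-specific modes | 39 | 32 | 0.94 |
| Common mode with 3 times their amplitude | 44 | 19 | 0.98 |
| Mode shapes differing between subjects to varying degrees | 6–27 | 1–15 | about 0.8–1.0 |
| One mode with half the power; moderate to large variation in shape, phase and amplitude | 17–20 | 11–14 | not computed |
| One mode with half the power; three levels of shape variation | 2–6 | 1–4 | not computed |

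The first two rows use noise, log-normal gain (SD 0.5) and three simulated studies per setting. In the third row the ratio moved further from 1 as shapes differed more. With the same mode shape in all subjects, at most 3% of eigenvalues were negative. Where negative eigenvalues total 15% of the trace, the positive ones total 100 + 15 = 115% of it.

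**Number of subjects and kind of median.** With 24 subjects and 256 channels, the structures in the first two rows gave 34–39% negative eigenvalues, totalling 12–19% of the trace, and a leading ratio of 0.92–0.99. With the median over 10 to 150 windows within one subject (32 or 64 channels), 23–41% were negative and the leading ratio was 0.94–1.00. The point therefore depends neither on 12 versus 24 nor on subjects versus windows.

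**Effect on the modes.** Over 18 settings with the first two structures (32 to 256 channels; 9, 12 or 24 subjects), the leading eigenvector of the median matrix agreed with that of the mean matrix (|cosine| 0.99–1.00). The leading ratio was 0.92–1.01, and the most negative eigenvalue averaged at most 6.5% of the leading one in size.

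**The case against.** The strongest reply is that the plan uses the decomposition to find principal modes and then tracks projected power. Projecting a subject's own spectral matrix onto any mode gives a non-negative value. Negative eigenvalues sit among trailing modes that the plan does not pursue, and the paragraph plans no share-of-power or coherence figure from the eigenvalue sum. All of this stands. What remains is that the text calls every eigenvalue a power, without condition, and that a leading eigenvalue can also be off.

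A second reply is that the median may not be entrywise. A geometric median is a weighted average of the inputs with non-negative weights and stays positive semidefinite. This is correct, but the plan does not say that it is meant, so the definition is needed either way.

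A third is that a median suits small EEG studies. This also stands. In simulation with one artifact-ridden subject, the median matrix kept the third mode (|cosine| about 0.9–0.98) while a trace-scaled mean lost it (about 0.1).

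A reader might go further and infer that the group modes and the permutation-tested projection are invalid, or that the median must give way to a mean. Neither follows. The leading modes were recovered about as well by the median as by the trace-scaled mean. The spread of one mode per subject into two tied leading modes in the exact example also occurs with the mean matrix (1.33, 1.33). Only the negative eigenvalue is specific to the median.

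**Conclusion.** The concern holds in a limited form. Under the entrywise reading, the statement that an eigenvalue is the power in its mode is not guaranteed; the exact example shows this without any assumption about the EEG. Trailing eigenvalues can be negative, and leading ones can differ from the power in the mode. That difference runs from near zero with a common mode shape to roughly 20% in the more heterogeneous settings simulated. These sizes, and the share of negative eigenvalues, reflect assumed structures and are not forecasts for this trial; 256 channels is also a maximum.

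The leading eigenvectors and the modal projection are little affected. The sample size rests on the Global Precedence score and is untouched. This is a correction to how mode power is computed and described, not a challenge to the mode analysis as a whole.

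**What to change.** In the eigenvalue and modal projection paragraph:

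1. State the type of median and whether it runs over subjects or windows. The median matrix may be kept to define the principal modes.
2. Do not report its eigenvalues as power. For each mode u and frequency f, compute u\*P_i(f)u from each subject's own matrix. If a share of power is wanted, divide by that subject's own trace. Summarise these non-negative values by the median across subjects.
3. Optionally, repeat the mode definition with the mean of trace-scaled matrices as a sensitivity analysis. It should not replace the median matrix, because it is less resistant to artifact.

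The cost is changed wording and a few lines of code. No new data are needed.
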